**(i) Background and objectives**

As many as 60% of breast cancer (BrCA) patients receiving radiation are known to develop fatigue with about 30% suffering persistent fatigue several months to years after treatment completion (12-23). The physical, psychological, and molecular mechanisms by which patients develop fatigue are poorly understood and most likely multi-factorial. One pathway that has received considerable attention is nuclear factor-kappa B (NF-kB)(24). The NF-kB pathway has emerged as having an important role not only in cancer treatment resistance but in the development of fatigue. NF-kB activation leads to over expression of interleukin (IL)-1beta, IL-6, and tumor necrosis factor (TNF)-alpha, all factors related to inflammation and factors that have been found to be upregulated in patients receiving radiation as well as BrCA survivors with fatigue (25-29). A recently published study looking at TNF-alpha, fatigue and cachexia in cancer patients receiving docetaxel showed that NF-kB is upregulated in fatigued patients and that agents which inhibit TNF-alpha lead to better tolerance of chemotherapy dose escalation (30). Work by our group and others has shown that ionizing radiation increases NF-kB pathway activity in circulating immune cells (as well as within breast cancer cells) and that this effect is most pronounced in women previously treated with chemotherapy (31, 32). Our work has shown that the NF-kB pathway activity in circulating immune cells is also related to fatigue development in BrCA patients treated with radiation and that patients most at risk for persistent fatigue and NF-kB pathway activity are those who have received chemotherapy for their breast cancer (31).

Curcumin, a known inhibitor of NF-kB, has been shown to decrease NF-kB activation in human participants. In a recent study, 8 grams of curcumin by mouth daily for 8 weeks was well tolerated in patients with pancreatic cancer and other pre-malignant conditions with no associated toxicities (6, 8). Although there is concern over the body's absorption of curcumin, the bioavailability of curcumin in the study of pancreatic cancer patients was shown, with peak drug levels at 22 to 41ng/mL that remained relatively constant over the first 4 weeks of treatment with 8 grams of curcumin daily (8). Clinical trials with daily dosages of 1,125 to 2,500mg have also confirmed the safety of curcumin and also shown its ability to decrease inflammation in patients with rheumatoid arthritis and in post-operative patients (6, 33, 34). In vivo murine models of chronic fatigue syndrome have also shown that curcumin may also alleviate symptoms of fatigue (35). While these studies are promising, very little is known about the capacity of Meriva to inhibit NF-kB in women treated for BrCA. We hypothesize that oral Meriva, a known inhibitor of NF-kB, may be used to decrease levels of NF-kB activity in BrCA patients previously treated with chemotherapy who go on to receive radiotherapy (XRT), a carefully chosen group of patients at particular risk for high levels of NF-kB DNA binding (a direct measure of NF-kB pathway activity).

We have chosen to administer oral Meriva, 500mg BID, in our patient population based on the above data. Meriva-500 is a curcumin formulation that also contains phosphatidylcholine, derived from soy that has been shown to aid in absorption of curcumin (9), permitting a lower overall dose of curcumin. Of note, 1000 mg Meriva contains 200 mg curcuminoids (>90% curcumin).

By decreasing activity of NF-kB, fatigue may improve in BrCA patients taking Meriva. Results from this study will contribute to the limited research available on the capacity of curcumin treatment, including Meriva, to inhibit NF-kB and its downstream mediators in vivo as well as symptoms of fatigue associated with excessive NF-kB pathway activity in BRCA patients.

**The primary objective of this protocol is to determine if Meriva reduces NF-kB DNA-binding and its downstream mediators in patients receiving XRT for their breast cancer after having completed chemotherapy.** Patients who have received prior chemotherapy will be eligible, because we have found that this enriched population is at particular risk for exhibiting increased NF-kB DNA binding following XRT. NF-kB DNA-binding is a direct measure of NF-kB pathway activity, while plasma concentrations of TNF-alpha and its soluble receptor sTNFR2, interleukin (IL)-1 receptor antagonist (IL-1ra), and C-reactive protein (CRP) are downstream indicators of NF-kB activity.

Secondary objectives will be to 1) determine if Meriva decreases levels of fatigue as measured by the Multidimensional Fatigue Inventory (MFI) in BRCA patients, and 2) determine longitudinal variances in skin changes measured by ultrasound in breast cancer patients undergoing XRT. Results from this study will contribute to the limited research available on the capacity of Meriva and curcumin to inhibit NF-kB and its downstream mediators in vivo.

### **(iii) Patients inclusion and exclusion criteria**

Female breast cancer patients over the age of 18 who were previously treated with standard anthracycline- and/or taxane-based chemotherapy will be recruited for this study. Patients enrolled in the study will meet standard criteria for whole breast XRT or chest wall XRT for patients who have had mastectomies. Patients will be included if they have a National Comprehensive Cancer Network score for fatigue over 3 (NCCN>3) as determined by the standard fatigue scale of 0-10 unless otherwise approved by the principle investigator or PI's designee. Participants will be excluded for medical conditions that are contraindications to XRT and/or might confound the relationship among fatigue and inflammation, including pregnancy, unstable major psychiatric disorders, autoimmune (active within the past 6 months) or inflammatory disorders, chronic infectious diseases (e.g. HIV, hepatitis B or C), neurologic disorders and uncontrolled cardiovascular, metabolic, pulmonary or renal disease (as determined by medical history, physical examination or laboratory testing) unless otherwise approved by the PI or PI's designee. Participants with an unstable major psychiatric disorder, as assessed by study clinician, or a diagnosis of Alcohol Abuse (more than 5 drinks in a 24 hour period) or Substance Dependence within the past 1 year (as determined by a standard psychiatric interview) will be excluded unless otherwise approved by the PI or PI's designee. Participants with an IDS score > 32 or IDS #18 score  $2_{\geq}$  will be referred to [name]. Participants with uncontrolled or chronic pain, a score greater than 4 on the standard pain scale, will be excluded unless otherwise approved by the principle investigator or PI's designee. Participants taking drugs known to affect the immune system (e.g. glucocorticoids, methotrexate, sulfasalazine and nonsteroidal anti-inflammatory agents) will also be excluded unless otherwise approved by the principle investigator or PI's designee. To protect against possible side effects of the study drug, women who are pregnant or nursing a child may not take part in this study. Subjects of childbearing ability must agree, with the study doctor, on a method of birth control to use throughout the study. Subjects who think they have gotten pregnant during the study must notify the study doctor immediately. Pregnant women will be taken out of the study. Patients using over the counter supplements or other natural products within one week of treatment, excluding vitamins and calcium supplementation, or at the discretion of the enrolling physician, will be excluded. Patients who have evidence of infection as determined by history, physical exam or laboratory testing (complete blood count and urinalysis) at baseline will be excluded unless otherwise approved by the PI or PI's designee.

Patients with anemia (HEM < 10g/dl) at baseline will be excluded unless otherwise approved by the PI or PI's designee. In addition, patients who develop evidence of infection (as determined by history, physical exam or laboratory testing) during the study will be discontinued from the study unless otherwise approved by the PI or PI's designee. Patients will be asked to refrain from having more than one alcoholic beverage per day.

This protocol proposes to enroll 60 total patients, with 30 randomized to the Meriva arm and 30 randomized to the placebo arm of the study.

[figure not shown]

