**Compliance:**

Patients will be asked to fill out a medication diary daily and report any missed doses during weekly telephone interviews. Patients who report taking less than 75% of their medication between interviews may be excluded from study participation at PI's discretion.

**Curcumin Visit III:** final evaluation of the last week of Meriva or placebo treatment

- Physician or NP evaluation or modified physical

- CBC with diff– review for infection and anemia
- Fasting blood draw for research ( two 4 ml purple tops, two 6 ml purple tops, and 1 tempus tube)
- Ultrasound scan and photographs at PI’s discretion
- Self-report of fatigue level and pain on a scale of 0-10, 0 being none and 10 being extreme.
- Inventory of Depressive Symptomatology – Self Reported (IDS- SR)[41], Pittsburgh Sleep Quality Index (PSQI)[42-45], Perceived Stress Scale (PSS)[46], Godin Leisure-Time Exercise Questionnaire (GLTEQ)[48], Multidimensional Fatigue Index (MFI) (36) and PROMIS Fatigue Short form [49]
- Collect unused medications and medication diary
- Patient reimbursement

During the screening visit Curcumin Visit 1, a urinalysis, CBC with differential, serum quantitative pregnancy test, and physician evaluation or modified physical by the study NP will be performed. A subset of patients may have an ultrasound scan and photographs done by Radiation-Oncology research team. The lab tests will be processed in the Emory Medical Laboratory (EML) system. The results of the evaluation or modified physical and urinalysis as well as the CBC with differential will be reviewed to rule out infection or anemia to verify eligibility. If infection or anemia or pregnancy is detected, the patient will be withdrawn from the study.

An ultrasound of the treated breast or chest wall and untreated breast and axilla may be performed at the baseline and final evaluation visits to assess cutaneous toxicity. These scans will be conducted based on the availability of research staff and space to conduct the scan. Each scan will take between 5 and 10 minutes to perform. Photographs of the treated breast (or chest wall) as well as the contralateral breast will also be taken. Ultrasound data and photographs will be stored in a computer for later review.

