**(xi) Potential risks and benefits to subjects:**

Potential risks: The risk to patients is minimal. Blood draws will be performed at two different time points during the course of this study.

All patients will be assigned a study number, and this number will be used in place of patient's names or identification numbers so there should be minimal risk of loss of patient confidentiality. The master sheet containing the patient number and study ID will be kept in a password protected database.

Curcumin doses up to 8 grams per day have been shown to be well tolerated with minimal side effects. It is not expected that curcumin doses proposed in this study will cause untoward adverse effects.

A recent literature review identified a study which suggested that curcumin may aggravate iron deficiency. However, patients will be screened for evidence of iron deficiency as evidenced by their hemoglobin and hematocrit. No patient with evidence of iron deficiency will be admitted to the study. All patients will be evaluated for evidence of iron deficiency upon completion of the study as per protocol.

Potential benefits: Patients undergoing this study may have improvement in their fatigue levels.

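### The anemia exclusion can be waived under section (iii) but means withdrawal under section (vi), and no scheduled test could show that a waived patient is free of the iron deficiency barred in section (xi)

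*Combined protocol and SAP*

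**What the plan says.** Three places in the combined protocol and SAP govern a low hemoglobin at entry.

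- **Section (iii), inclusion and exclusion criteria:** "Patients with anemia (HEM < 10g/dl) at baseline will be excluded unless otherwise approved by the PI"; the sentence goes on to give the PI's designee the same power.
- **Section (vi), the paragraph on the screening visit (after the Visit III list):** the results of the physical and urinalysis "as well as the CBC with differential will be reviewed to rule out infection or anemia to verify eligibility". The paragraph ends: "If infection or anemia or pregnancy is detected, the patient will be withdrawn from the study".
- **Section (xi), potential risks:** "A recent literature review identified a study which suggested that curcumin may aggravate iron deficiency". The stated safeguard is that "patients will be screened for evidence of iron deficiency as evidenced by their hemoglobin and hematocrit", followed by "No patient with evidence of iron deficiency will be admitted to the study". A later check is also promised: "All patients will be evaluated for evidence of iron deficiency upon completion of the study as per protocol".

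The Visit I list and the Curcumin Study Checklist show a CBC with differential, a urinalysis and a serum pregnancy test at screening. Neither lists an iron test. After screening, the next scheduled CBC is at Visit III, described as the "final evaluation of the last week of Meriva or placebo treatment", or at an early termination visit if there is one.

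**The concern.** Staff holding a screening CBC with hemoglobin below 10 g/dl are given two different instructions. Section (iii) lets the patient in if the PI or designee agrees. Section (vi) takes her out and mentions no approval. Once an approval has been given, both cannot be followed.

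The mismatch has some weight because low hemoglobin is linked to a risk of the study drug that the protocol itself names. Section (xi) answers that risk with an entry bar that has no exception, and it reads iron status from the same blood count that section (iii) allows the PI to set aside. At stake is whether the safeguard described in section (xi) works when an exception is approved.

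**Working it through.** No arithmetic applies: the point does not depend on sample size, power or alpha. The check sets the three rules side by side and runs patients through them. HEM is read as hemoglobin, as its units suggest.

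| Place | Finding | Threshold given | Exception given | Consequence |
|---|---|---|---|---|
| Section (iii) | Anemia | HEM < 10 g/dl | Yes, PI or designee | Excluded unless approved |
| Section (vi) | Anemia | None | None | Withdrawn |
| Section (xi) | Evidence of iron deficiency, from hemoglobin and hematocrit | None | None | Not admitted |

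**Patient A: below 10 g/dl, no approval given.** Sections (iii) and (vi) both keep her out. There is no conflict.

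**Patient B: below 10 g/dl, approval given.** Section (iii) admits her and section (vi) withdraws her. This is a direct conflict. Section (xi) also bars her if her low hemoglobin is taken as evidence of iron deficiency. It sets no cut-off, so that step is a matter of reading.

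**Patient C: slightly above 10 g/dl.** Section (iii) admits her. Section (vi) is unclear because it does not say what counts as anemia. Section (xi) is unclear for the same reason.

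**Could the PI separate a safe exception from an unsafe one?** The inputs that the protocol supplies are the screening CBC, the urinalysis, the pregnancy test and the clinical evaluation. Research blood is drawn for inflammatory markers, NF-kB binding and gene expression. None of these is an iron study. The only stated evidence on iron deficiency is hemoglobin and hematocrit, which is the result being waived. So no protocol-specified test can show that patient B's anemia has another cause.

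**Is the section (vi) rule silently subject to the section (iii) approval?** Section (iii) repeats the approval wording in most of its individual criteria, whereas sections (vi) and (xi) omit it. The grouping in section (vi) does not settle the matter. Anemia stands there beside infection, which section (iii) makes waivable, and beside pregnancy, which section (iii) also bars in a separate sentence with no exception.

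**The case against.** The best case for the plan is that the texts can be reconciled. Section (iii) is the eligibility section and the only place that defines anemia. A reader of section (vi) must go there for the meaning of the term and finds the approval clause in the same sentence. PI approval is also the general pattern across the criteria. On this view section (vi) is a shorthand summary, and section (xi) acts as a limit on the approval: if hemoglobin below 10 g/dl counts as evidence of iron deficiency, the patient is barred whatever section (iii) allows. That reading is possible, and it is why the point is minor. But section (vi) does not say it, and staff should not have to infer it.

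It is also fair that an exception needs a deliberate decision by the PI or designee. The risk itself rests on one study that section (xi) mentions without a reference, dose or effect size. Weekly calls review adverse events and can bring a patient in for an examination. All of this stands and limits the weight of the point.

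Four stronger readings are tempting, and the documents do not support them:

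- **That section (xi) flatly contradicts section (iii).** Anemia and iron deficiency are different conditions, and section (xi) gives no cut-off. The direct conflict is between sections (iii) and (vi).
- **That time on drug before the next scheduled CBC measures the harm.** If Visit III falls in the last of about six treatment weeks, that time is 5 × 7 = 35 to 6 × 7 = 42 days. This is ordinary exposure, the same for every participant who completes treatment, and the fix does not shorten it. The lower figure is itself an assumption, since section (iv) places the final visit only within the six-week period.
- **That the infection waiver should go too.** Section (iii) and section (vi) differ on baseline infection in the same way. No drug-related harm can be argued from the documents, though, and removing that waiver would leave baseline infection unwaivable while infection arising on study stays waivable.
- **That the primary comparison is affected.** Nothing in the documents shows this.

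**Conclusion.** The inconsistency is real and lies in the current text. A patient with hemoglobin below 10 g/dl who is approved under section (iii) cannot also satisfy section (vi). The approval also weakens the protocol's own answer to a named drug risk, because no scheduled iron test could show that the approved patient is free of iron deficiency.

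It is a minor safety and eligibility matter. How many patients would be approved, and how far hemoglobin might fall in any of them, cannot be estimated from the documents. The conclusion assumes that section (vi) means what it says, without an implied exception. The link to section (xi) further assumes that low hemoglobin may be read as evidence of iron deficiency, which fits the way that section says it will screen. If an implied exception was intended, the conflict becomes an ambiguity, and the text still needs to be clarified.

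**What to change.** Make two edits:

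1. In section (iii), delete from the anemia sentence the clause that lets the PI or designee approve exceptions, so that HEM < 10 g/dl at baseline excludes outright.
2. In section (vi), have the screening paragraph refer to that same HEM < 10 g/dl criterion, so that the withdrawal rule has a defined trigger.

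Leave the section (xi) bar as it stands, as an additional limit. It should not be redefined as 10 g/dl, because it may also keep out patients above that value. How it applies to them remains a clinical judgement that these edits do not settle.

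A cross-reference in section (vi) that keeps the approval would also remove the conflict between sections (iii) and (vi). Keeping exceptions safely, however, would call for an iron test before approval and a CBC during treatment, and neither is scheduled. Deletion is the smaller change and agrees with the other two sections.

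The cost is one deleted clause and one cross-reference, with no new test or visit. The downside is the loss of a few patients who might have been approved.

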#### (iv) Design

This double-blind, placebo controlled, randomized clinical trial will enroll BrCA patients seen at the Emory Breast Centers (Winship Cancer Institute of Emory University and Emory University Hospital Midtown) or in the community for XRT who were previously treated with chemotherapy. These patients will be approached for enrollment on this therapeutic study during the first three weeks of receiving radiation therapy or one to three months post XRT.

In patients previously treated with chemotherapy, we will administer placebo or Meriva daily for approximately 6 weeks, beginning immediately after the completion of XRT or up to 3 months post-XRT. Patients will be randomized to placebo or Meriva-500 (500 mg PO BID) using a computerized system under the control of Emory Pharmacy. Randomization will occur in blocks of 10. Meriva-500 will be obtained from Thorne Research. Blood will be drawn at baseline and at the first follow-up appointment to determine NF-kB DNA-binding in peripheral blood mononuclear cells, expression of NF-kB regulated genes, and plasma cytokine concentrations. The final study visit will occur during the 6 week treatment period. Study Coordinator will make an effort to coincide the follow up visit and six week post-radiation follow up visit. Because placebo or Meriva is being given after XRT is complete, it is unlikely to alter the efficacy of the XRT or enhance side effects of XRT.

Thirty patients will be enrolled per arm. NF-kB DNA-binding, downstream mediators of NF-kB activity and microarray analysis of NF-kB regulated genes will be used to determine NF-kB pathway activation. If any of these measures of NF-kB DNA binding activity (the primary outcome variables)

**Patients will receive daily Meriva treatment for approximately 6 weeks beginning immediately after radiation therapy (XRT) or up to 3 months post-XRT. Peripheral blood will be drawn during the last week of XRT and again after 6 weeks of Meriva (or Placebo) for assessment of NF-kB pathway activation.**

decrease to the mean level of non-chemotherapy treated women who receive XRT, the 500 mg BID dose level will be considered successful.

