#### (vi) Observations and measurements

Based on work performed in prior studies, we do not anticipate biomarker responses that would suggest adverse reactions to Meriva (1-4). We will therefore not collect blood samples during the 6 week treatment with Meriva to monitor adverse biomarker responses. Research blood will be collected at baseline during the last week of XRT or up to three months post XRT and at the conclusion of the 6 weeks treatment with Meriva. Patients will be interviewed weekly by phone to ensure they are not experiencing side effects previously described for curcumin, including nausea and diarrhea. If they do report worsening of these symptoms compared to before they started Meriva, they will be asked to immediately discontinue taking Meriva and come to the clinic for full physical evaluation. In the case that a patient experiences adverse side effects and stops taking Meriva, self-report information and blood samples will still be collected at the early termination visit.

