#### Curcumin Visit I: Screening

- Information regarding disease characteristics (including stage, tumor size, grade)
- Patient demographics (including age, race, co-morbidities, social history)
- Systemic treatment (including hormone therapy, systemic therapy), surgical treatment, and radiation treatment will be collected and recorded.
- Informed consent process
- Physician or NP evaluation or modified physical
- CBC with diff
- Serum quantitative pregnancy test
- Urinalysis with microscopy
- Self-report of fatigue level and pain on a scale of 0-10, 0 being none and 10 being extreme. The patient's self-report of fatigue at these visits will be used to assess the grade of their fatigue.
- Inventory of Depressive Symptomatology – Self Reported (IDS-SR)[41]- Participants with an IDS score > 32 or a score of 2 or higher on IDS item #18 will be referred to [name]
- PROMIS Fatigue Short form [49]
- Patient reimbursement
- Review labs for infection and anemia

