#### Curcumin Visit II: Baseline (XRT end – last week of XRT or within 3 months after)

- Inclusion criteria completed

[figure not shown]
- Mediterranean diet survey, Inventory of Depressive Symptomatology – Self Reported (IDS-SR)[41], Pittsburgh Sleep Quality Index (PSQI) [42-45], Perceived Stress Scale (PSS)[46], Godin Leisure-Time Exercise Questionnaire (GLTEQ)[48], Multidimensional Fatigue Index (MFI) (36) and PROMIS Fatigue Short form [49]
- Self-report of fatigue level and pain on a scale of 0-10, 0 being none and 10 being extreme.
- Fasting blood draw for research (two 4 ml purple tops, two 6 ml purple tops, and 1 tempus tube)
- Ultrasound scan and photographs at PI's discretion
- Randomization
- Dispense medications and medication diary
- Patient reimbursement

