### Analytical Plan

Power analysis: Based on a preliminary data, the mean change of NF-kB DNA binding from baseline among patients who underwent six weeks XRT was 8.2 ng NF-kB per assay well (SD = 9.0). We hypothesize that in this study the patients in the placebo group will have the similar response as in the preliminary data, and patients who receive Meriva, the mean change of NF-kB DNA-binding level from baseline to 6 weeks post XRT is 0.0 with a reduced SD of 4.5. Based on alpha of 0.05 and a n = 11 per group, we will have 82% power to detect the above hypothesized difference by one-sided two-sample t test. We believe such a difference is clinically meaningful and is well within the range of differences observed in chemotherapy vs. no chemotherapy patients and fatigued vs. non-fatigued patients.

Statistical analysis plan: Primary objectives: the mean changes of NF-kB DNA binding from baseline to Week 6 will be compared between two groups using two-sample t test. The change of plasma concentration of NF-kB downstream mediators from baseline will be compared between two groups using two-sample t-test/Wilcox sum rank test for continuous measures and using Chi-square test/Fisher's exact test for categorical measures. Secondary objectives: The change of MFI over time in two groups will be compared by the GEE model.

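### Baseline can fall anywhere from the last week of radiation to three months after it, yet no stratification or adjustment for time since radiation is stated, which costs precision and leaves chance imbalance uncorrected

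*Combined protocol and SAP*

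**What the plan says.** Section (iv) Design approaches patients "during the first three weeks of receiving radiation therapy or one to three months post XRT" and has treatment "beginning immediately after the completion of XRT or up to 3 months post-XRT". Section (vi) Observations and measurements gives the sampling window: "Research blood will be collected at baseline during the last week of XRT or up to three months post XRT". The Visit II heading agrees: "XRT end – last week of XRT or within 3 months after". The boxed text in section (iv) is narrower and places the first blood draw in the last week of XRT only. That conflicts with section (vi) and Visit II, and the passages must be reconciled.

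On allocation, section (iv) says "Randomization will occur in blocks of 10" and names no stratification factor.

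On analysis, the Analytical Plan states that "the mean changes of NF-kB DNA binding from baseline to Week 6 will be compared between two groups using two-sample t test". The plasma mediators get two-group tests on change, and the MFI gets a GEE with no covariates named.

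At Visit I, information on "surgical treatment, and radiation treatment will be collected and recorded". No last-fraction date is specified.

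**The concern.** The outcomes are six-week changes. One woman may have her baseline while still being irradiated and another up to three months later. The protocol itself gives reasons to think that timing relative to radiation matters. Section (i) says radiation raises NF-kB activity. Section (v) picks six weeks because a rise in NF-kB activity related to fatigue was seen over that period. The power paragraph uses a mean rise of 8.2 across six weeks of XRT. On fatigue, section (i) reports that as many as 60% develop it, "with about 30% suffering persistent fatigue several months to years after treatment completion".

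If untreated change depends on time since XRT, an unadjusted test leaves that variation in the error term. An uneven split of early and late starters between arms would then move the estimate in that trial, with nothing in the analysis to correct it.

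**Working it through.** **Inputs from the documents.** 30 per arm (section (iii)); placebo change 8.2, SD 9.0; Meriva change 0.0, SD 4.5; n = 11 per group, one-sided alpha 0.05, 82% power (Analytical Plan).

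**Inputs that must be assumed.** The share p of late starters, and the gap G between early and late starters in expected untreated change. The documents give neither.

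**1. The stated power reproduces.** Root-mean-square SD = √((9.0² + 4.5²)/2) = √50.625 = 7.115. Noncentrality at n = 11 is 8.2/(7.115·√(2/11)) = 2.70. The noncentral t gives 82.4% with Welch degrees of freedom and 83.3% with 20, against a stated 82%. This calculation assumes one homogeneous placebo change.

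**2. Chance imbalance.** A 20-point difference is 6 patients out of 30.
- 10% late (6 of 60): all six must fall in one arm, so the probability is 2·C(30,6)/C(60,6) = 2·593,775/50,063,860 = 2.4%.
- 30% late: 16% with 18 late patients split at random between arms; 12% if each patient is late independently.
- 50% late: 20% and about 15% on the same two models.

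The small effect of blocking is ignored. A 20-point imbalance shifts that trial's estimate by 0.20·G, which is 0.82 for G = 4.1 and 1.64 for G = 8.2.

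**3. Precision from a nominal 80%.** Let g be the gap in within-group SDs. The unadjusted variance is inflated by 1 + p(1−p)g². With 30 per arm, a two-sided 5% test and unadjusted power set to 80%, the adjusted power is:

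| Late share | g = 0.5 | g = 0.91 (8.2/9.0) | g = 1.0 |
|---|---|---|---|
| 10% | 81% (inflation 2%) | 83% (7%) | 83% (9%) |
| 30% | 82% (5%) | 86% (17%) | 87% (21%) |
| 50% | 82% (6%) | 87% (21%) | 88% (25%) |

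**4. Precision at the plan's own effect and SDs.** Add p(1−p)G² to each arm's variance. With p = 0.5 and G = 8.2 this is 0.25·67.24 = 16.81, or 33% of 50.625. (The 21% in the table is the same quantity over 9.0² = 81.)

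| Scenario, p = 0.5 | G = 0 | G = 4.1 | G = 8.2 |
|---|---|---|---|
| Effect 8.2, 30 per arm, one-sided | 99.7% | 99.5% | 98.5% |
| Effect 8.2, 30 per arm, two-sided | 99.2% | 98.7% | 96.6% |
| Effect 8.2, 11 per arm, one-sided | 82.4% | 79.8% | 72.6% |
| Effect 4.1, 30 per arm, two-sided | 59% | 56% | 47% |

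In simulation of the last row (blocks of 10, 5,000 runs per scenario), adjusting for early or late start held power at 58–60%.

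**5. Validity.** In the same simulations with no drug effect, two-sided type I error was 5.1–5.2% unadjusted and 5.2–5.7% adjusted, for G from 0 to 8.2.

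**The case against.** The strongest reply is that this is optional efficiency. Randomisation protects the comparison, chance imbalance is already covered by alpha, and at the planned effect with 30 per arm almost nothing is lost. If most women enter at the end of XRT, as the boxed text and the effort to align the final visit with the six-week post-radiation visit suggest, the gain from 80% is only to 81–83%. All of this stands, and it limits the weight of the point. So does the brevity of the GEE sentence: silence on covariates there is not a decision to exclude them.

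A reader might also infer more than the documents support:

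- *Early starters begin at a radiation peak and then recover.* No section says NF-kB falls after XRT. The power paragraph assumes that placebo patients rise by 8.2 up to six weeks after it.
- *The 60% and 30% figures prove a difference between early and late starters.* They describe irradiated patients generally, over months to years. This trial requires a fatigue score over 3 unless waived, whenever the patient enters.
- *The two approach windows define two baseline groups.* Nothing ties a patient approached during XRT to a last-week baseline; treatment may start up to three months later. A two-level route covariate could misclassify patients.
- *The 8.2 measures the gap.* It is a change across XRT, used here only to set a range.

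The reply does not remove the case for adjusting. The 99.7% rests on the full planned effect and on measurable NF-kB samples; section (v) reports that NF-kB binding could not be measured in the first 10 completers. The Analytical Plan gives no power calculation for the mediators or the MFI.

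**Conclusion.** The point holds as one about precision and chance imbalance. It does not show bias or an inflated false-positive rate. Entry timing varies by up to about three months on a factor that the protocol links to its outcomes, and no stratification or adjustment for it is stated.

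The size depends on two quantities the documents do not give, and the direction of any gap is also unknown. For gaps of 0.5 to 1.0 SD and late shares of 10% to 50%, adjustment lifts a nominal 80% power to about 81–88%. At the planned 8.2 with 30 per arm, the loss from not adjusting is about one percentage point one-sided, even at a gap of 8.2 and a 50% share. The benefit lies mainly in smaller effects, the mediators, the MFI, and an NF-kB comparison with few usable samples. If there is no gap, adjustment gains nothing and costs almost nothing.

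**What to change.** Before unblinding, prespecify weeks from the last XRT fraction to Visit II as a continuous covariate, negative or zero if the patient is still on XRT. Do not use approach route. Fit a linear model for change in NF-kB binding and in each plasma mediator, with arm and this covariate. A rank-sum test takes no covariate, so skewed mediators would need a transformed scale. In the MFI GEE, if both visits are modelled as outcomes, include the covariate's interaction with visit, so that it adjusts the change and not only the level. Keep the unadjusted tests as a sensitivity analysis.

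Confirm that the XRT end date is recorded for every patient. Visit I promises only radiation treatment information, and for anyone screened during XRT that date still lies ahead. Reconcile the boxed text in section (iv) with the wider baseline window in section (vi) and Visit II.

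The cost is a short addition to the Analytical Plan, one degree of freedom in each linear model, and one date per patient. If enrolment is still open, stratifying the remaining randomisation by baseline timing is optional.
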